8.2.2. Summary of Analyses

Endpoint	Time points	Analysis Set	Statistical Method	Model/ Covariates/ Strata	Missing Data	Objective
Summary of total joint replacement (TJR) and adjudication outcomes (Joint Level)	Any time during parent study or 1064	SAS	None	N/A	Observed	Summary of frequency and the proportion
Summary of detail of adjudication outcomes (Joint Level)	Any time during parent study or 1064	SAS	None	N/A	Observed	Summary of frequency and the proportion
Summary of total joint replacement (TJR) and adjudication outcomes (Subject Level)	Any time during parent study or 1064	SAS	None	N/A	Observed	Summary of frequency and the proportion
Summary of detail of adjudication outcomes (Subject Level)	Any time during parent study or 1064	SAS	None	N/A	Observed	Summary of frequency and the proportion
Surgeon's assessment of procedural difficulty by TJR joint and total (All OA parent studies)	Assessed after surgery	SAS	None	N/A	Observed	Summary of surgical outcome
Subject's overall satisfaction with surgery by TJR joint and Total (All OA parent studies)	Week 4, 12, 24	SAS	None	N/A	Observed	% and frequency of each category
Subject's overall satisfaction with surgery by TJR joint and Total (All OA parent studies)	Week 4, 12, 24 and 24 (LOCF)	SAS	None	N/A	Observed (LOCF for Week 24 (LOCF))	Summary of surgical outcome
Physical rehabilitation in relation to replaced joint by TJR joint and Total (All OA parent studies)	Any time post-surgery	SAS	None	N/A	Observed	Summary of surgical outcome
Additional or corrective procedures relating to TJR by TJR joint and Total (All OA parent studies)	Any time post-surgery	SAS	None	N/A	Observed	

Endpoint	Time points	Analysis Set	Statistical Method	Model/ Covariates/ Strata	Missing Data	Objective
Average Pain in the joint to be replaced/replaced joint by visit and change from BL by TJR joint and Total (All OA parent studies)	BL, Week 4, 12, 24, 24 (LOCF)	SAS	None	N/A	Observed (LOCF for Week 24 (LOCF))	Summary of surgical outcome
WOMAC Pain, Physical Function and Stiffness subscales by visit and change from BL by TJR joint [Hip/Knee] and Total (All OA parent studies)	BL, Week 4, 12, 24, 24 (LOCF)	SAS	None	N/A	Observed (LOCF for Week 24 (LOCF))	Summary of surgical outcome
SPADI dimensions and total by visit and change from BL (All OA parent studies)	BL, Week 4, 12, 24, 24 (LOCF)	SAS	None	N/A	Observed (LOCF for Week 24 (LOCF))	Summary of surgical outcome
Post-surgical complications (All OA parent studies)	Any time post-surgery	SAS	None	N/A	Observed	
Concomitant analgesic medication use (All OA parent studies)	Any time post-surgery	SAS	None	N/A	Observed	Summary of surgical outcome
Subpopulation summary of Surgeon's Assessment of Procedural Difficulty for subjects who had RPOA (type 1 and type2), RPOA (type 1), RPOA (type 2), primary ON, SIF, or NPOA	BL, Week 4, 12, 24, 24 (LOCF)	SAS	None	N/A	Observed	Subgroup presentation
Subpopulation summary of Subject's Overall Satisfaction for subjects who had RPOA (type 1 and type2), RPOA (type 1), RPOA (type 2), primary ON, SIF, or NPOA	BL, Week 4, 12, 24, 24 (LOCF)	SAS	None	N/A	Observed	Subgroup presentation

Endpoint	Time points	Analysis Set	Statistical Method	Model/ Covariates/ Strata	Missing Data	Objective
Subpopulation summary of concomitant nondrug treatment for subjects who had RPOA (type 1 and type2), RPOA (type 1), RPOA (type 2), primary ON, SIF, or NPOA	Any time post-surgery	SAS	None	N/A	Observed	Subgroup presentation

SAS: Safety analysis set for subjects with TJR and entered into 1064

9. REFERENCES

N/A.

10. APPENDICES

Appendix 1. DATA DERIVATION DETAILS

Appendix 1.1. Definition and Use of Visit Windows in Reporting

Study visits/telephone contacts are planned at Baseline, Day of Surgery (Day 1, with assessments made by the surgeon within 10 days after the date of surgery), and Weeks 4, 8, 12, 16, 20 and 24. Information relating to the post-operative outcome measures is collected at Weeks 4, 12 and 24, and it is for these visits that windows will be defined. If a subject discontinues from the trial then the Week 24/Early termination visit assessments will be completed.

When multiple observations occur in a visit window, the observation closest to the protocol specified target day will be used, noting that the latter will be used in the case of a tie.

Visit	Target Study Day	Window
Baseline	Variable	[No lower limit, Day -1]
Day of Surgery	1	N/A
Week 4	29	[2,57]
Week 12	85	[58,127]
Week 24	169	[128, No upper limit]

Appendix 2. UNBLINDING PLAN

1. Introduction

The A4091064 is the long-term observational study without dosing to follow up subjects who undergo total joint replacement (TJR) of knee, hip or shoulder from one of parent studies (A4091056, A4091057, or A4091058) or sub-studies (A4091059, A4091061, or A4091063), and one of the secondary objectives is to compare the post-operative outcomes for tanezumab 2.5mg and 5 mg versus NSAIDs for subjects who underwent a TJR in A4091058.

The purpose of this unblinding plan is to describe who can access to the unblinding information of parent phase 3 studies (and sub-studies) while A4091064 is ongoing and the rationale. The goal is to maintain the double blind (subjects and investigator) at any study sites and among operational colleagues interacting with site directly about patient data in order to minimize the potential to introduce bias for comparison of the post-operative outcomes.

2. Rationale for Unblinding of Parent Phase 3 Studies to A4091064 Study Team Members

The rationale for the appropriateness of this approach for unblinding includes the following:

- Major endpoints to evaluate TJR follow-up of A4091064 are based on patient and/or surgeon reported outcomes, and an investigator or Pfizer study team will not evaluate them.
- All endpoints of A4091064 will be summarized descriptively and there is no formal hypothesis testing.
- A4091064 is a study being incorporated into the data package for regulatory submission. Pfizer team needs to evaluate TJR based on the data of both A4091064 and these parent studies (and sub-studies) simultaneously with considering these relationships by representatives who are familiar with these studies.
- No changes will be made to A4091064 study designs, conduct, or analysis based on the parent phase 3 studies unless the program is terminated or otherwise modified for safety findings, in which case, the changes would be reflected in a protocol amendment.

3. Unblinding Prior to Database Release of any Parent Phase 3 Studies

The phase 3 program is using a safety monitoring committee (SMC), which will have access to unblinded data throughout the parent phase 3 studies for the monitoring of subject safety. A separate SMC charter specifies the role and responsibilities of the SMC and the contact individuals within the Pfizer's organization and the SMC responsible for communication between these organizations.

4. At or after Database Release of any Parent Phase 3 Studies

This section describes who remains blind and who will become unblinded at or after database release of any parent phase 3 studies for A4091064 evaluation. The process of unblinding follows the following standard of procedure:

- Pfizer: DMB08 (Study Data Set Review, Release, and Archive)

4.1 Unblinded at or after Database Release

Following database release for phase 3 parent studies, unblinding of each parent study (and sub-studies) will occur at the individual subject level as well as at the summary (ie, treatment group) level to the A4091064 team members who are NOT defined as colleagues who remain blind in the section 4.2.

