5. STUDY TREATMENTS

This is an observational study of subjects who were randomized and treated in tanezumab Study A4091056, A4091057 or A4091058 and who subsequently underwent a total knee, hip or shoulder replacement during the treatment or safety follow-up period. Any subject with a qualifying total joint replacement after the last subject in the study completes the treatment period in studies A4091059, A4091061 or A4091063 may also be followed in this study (A4091064).

There are no protocol defined study medications in this observational study.

Subjects, investigators, study coordinators, clinical site staff, orthopedic surgeons, clinical research associates (CRAs) and staff directly involved with this study at Pfizer and its designees will be blinded to treatment assignment in the parent study (ie, Study A4091056, A4091057, A4091058 or other tanezumab study).

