At the Week 4, 12 and 24 post-surgery telephone contacts, subjects will be queried for rehabilitation activities related to the replaced joint. Specifically, subjects will be asked to respond yes or no to the following question:

- *Are you participating in physical rehabilitation activities related to your replaced joint?*

Subjects will be queried for details if the answer to the question is yes.

The data relating to the endpoints of physical rehabilitation, or additional or corrective procedure, related to the replaced joint up to Week 24 will be derived from an ongoing clinical review of the concomitant non-drug treatment/procedure case report form (CRF) page. This review will identify treatments that are relevant for these endpoints, and a log of such data will be maintained. The data relating to the endpoint of concomitant analgesic medication use will be derived from an ongoing review of the concomitant analgesic drug CRF page. These reviews will be made during the study and data will be finalized prior to the database release for this study.

Events identified as the first symptom leading to total joint replacement will be reviewed and determined prior to the unblinding for the respective parent study.

The list of post-surgical complications will be derived from reported adverse events and will consist of complications that are clinically significant and attributable to the total arthroplasty procedure eg, periprosthetic joint infection/wound infection, periprosthetic fracture, pulmonary embolism or sepsis/septicemia/shock. The list of post-surgical complications will be developed during Study A4091064 and finalized prior to Study A4091058 unblinding. Other adverse events may be identified as post-surgical complications after the unblinding of the Study A4091058 database. These events will also be summarized as complications, and will be noted as having been included in the list after the unblinding of the Study A4091058 database.

Adverse Events which are “treatment emergent” in relation to the Baseline study day will be reported overall and by prior study treatment group. Adverse events ongoing from the parent study will continue to be followed in this study. They will not be included in incidence tables from this study unless the severity worsens.

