4.2 Blinded until Database Release of final phase 3 study

At the time of database release/unblinding for reporting of each parent study, Pfizer/Syneos/EPS roles of A4091064 study in below lists are to remain blinded of individual subject level in order to maintain the integrity of the blinding to subjects and investigators;

- Pfizer: Clinician interacting with site directly for TJR evaluation, and regional clinical site lead (RCSL);
- Syneos/EPS(Japan Local CRO): Clinical research associate, monitoring lead, CTA, and CMPL.

An investigator site (investigators, and all other site staff) participating in A4091064 is to remain blinded to individual subject treatment assignment until all subjects in the site will be finished A4091064 and until all data for these subjects will be cleaned.

Pfizer SOPs CT20 (Public Disclosure of Pfizer Clinical Study Data and Authorship) and DMB10 (Clinical Study Report) require unblinded results to be provided to study sites after the trial has completed. Some amendment/deviation may be applied to delay sending results from the parent studies or sub-studies until a site has completed participation of all subjects in the site of A4091064.

Selected investigators may be required to review an interim CSR for A4091064 in order to sign the Investigator's Declaration. In order to minimize any potential bias after unblinding of any parent study, an investigator will be selected who would not have any on-going A4091064 subjects at the time of the investigator's review of an interim A4091064 CSR.

It is also recognized that unblinded summary results may become publicly known through press release, presentations at scientific conference, publication and so on.

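### SAP Appendix 2 unblinds part of the A4091064 team to individual parent treatment, contrary to Protocol 5, while reviews that decide co-equal endpoints stay open with no requirement for blinded reviewers

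*SAP*

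**What the plan says.** Protocol section 5 lists who is kept unaware of the parent-study arm. Besides subjects, sites and surgeons, it says that "staff directly involved with this study at Pfizer and its designees will be blinded to treatment assignment in the parent study". It gives no end date and does not narrow the group to people who deal with sites.

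SAP Appendix 2 sets out to "describe who can access to the unblinding information of parent phase 3 studies (and sub-studies) while A4091064 is ongoing". Its section 4.1 says that after parent database release, unblinding "will occur at the individual subject level as well as at the summary (ie, treatment group) level to the A4091064 team members". The only exception is for the roles that section 4.2 keeps blind: on the sponsor side, the clinician who deals with sites about the joint replacement and the regional site lead; on the contractor side, the research associate, monitoring lead, CTA and CMPL. The heading of section 4.2 reads "Blinded until Database Release of final phase 3 study". Sites stay blind until their own A4091064 subjects have finished and the data are cleaned.

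The first reason given for this arrangement (Appendix 2, section 2) is that the major endpoints are reported by patients or surgeons and "an investigator or Pfizer study team will not evaluate them".

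SAP 6.1 describes how three endpoints are built. Rehabilitation and additional or corrective procedures come from a continuing clinical review of the non-drug treatment and procedure page, which picks out the relevant entries and logs them. Analgesic use comes from a continuing review of the analgesic page. On timing it says: "These reviews will be made during the study and data will be finalized prior to the database release for this study".

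**The concern.** Two things do not fit together. The protocol promises a blind that the SAP partly removes during the study. The first reason offered for removing it also does not clearly apply to endpoints whose content is settled by a review.

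Whether a listed treatment is rehabilitation of the replaced joint, or whether a procedure is corrective and related to that joint, can need judgement. If the person deciding knows the arm, that judgement can differ by arm without anyone intending it. The secondary objective compares tanezumab 2.5 mg and 5 mg with NSAID in A4091058. Appendix 2 itself says that its aim is to limit bias in comparing post-operative outcomes. A difference introduced at classification could not be recognised later unless unblinded decisions were marked as such.

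**Working it through.** No alpha, power or sample-size figure bears on this point. The check is a side-by-side reading, two counts and a timeline.

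**1. Who is blind, and until when**

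| Place | Who | Blind ends |
|---|---|---|
| Protocol 5 | Sites, surgeons, CRAs, and sponsor and designee staff working directly on the study | Not stated |
| SAP 3 | Information from A4091064 generally | When the parent study is unblinded |
| SAP Appendix 2, section 4.1 | Team members outside the section 4.2 list | Parent database release |
| SAP Appendix 2, section 4.2 | Listed sponsor and contractor roles | Release of the final phase 3 study |
| SAP Appendix 2, section 4.2 | Sites | Site's A4091064 subjects finished and data cleaned |

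The first and third rows conflict on their face. The fourth is ambiguous: A4091064 is itself called a Phase 3 study (Protocol 3, SAP 2.1), but Appendix 2 mostly uses the phrase for the parent studies. On the parent-study reading, site-facing staff could be unblinded while their sites must stay blind.

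**2. How many endpoints are affected.** SAP 6.1 lists 9 co-equal endpoints: surgeon's assessment, satisfaction, complications, additional or corrective procedures, rehabilitation, pain, WOMAC, SPADI and analgesic use. Three are derived by the reviews above, so 3 of 9. The judgement involved is not equal: analgesic entries already sit on a dedicated page.

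**3. When comparable decisions close (SAP 6.1)**
- First-symptom events: before unblinding of the respective parent study.
- Complication list: before A4091058 unblinding, with later additions marked as such.
- The three reviews: before A4091064 database release only. The non-drug page has a log, but no flag for decisions made after unblinding is required.

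**4. Possible overlap in A4091058.** Total parent duration is 80 weeks (Protocol 1.2.3.1) and follow-up is 24 weeks after surgery (Protocol 3). Take the last-enrolled subject, and let release come L weeks after that subject's last parent visit. L is not given; assume 0 to 24.
- Surgery at week 80: follow-up ends at 80 + 24 = 104. Overlap = 104 - (80 + L) = 24 - L, so 24 down to 0 weeks.
- Surgery at week 56, the end of treatment: 56 + 24 = 80, and 80 - (80 + L) = -L, so no overlap.
- Surgery only planned at the last parent visit: longer than the first case.

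This bounds new data only. An entry collected before release can still be reviewed after it, because the reviews close at A4091064 database release.

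**5. Weight of one decision.** Enrolment is estimated at below 250 in all (Protocol 9.1) and the split by arm is unknown. Assume 30 to 60 per A4091058 arm (3 x 30 = 90 and 3 x 60 = 180, both below 250). One reclassified subject moves an arm's percentage by 1/30 = 3.3 points to 1/60 = 1.7 points.

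**6. By-arm results before the reviews close.** SAP 3 allows an interim analysis for a submission once the parent studies are unblinded, and Appendix 2 section 4.2 foresees an interim A4091064 report. Arm-level results could therefore be known while later entries are still being classified.

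**The case against.** The case for the plan has several sound parts.

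- **The reviewer is not named.** A reader might infer that an unblinded sponsor team does the reviews. The documents do not say so. The site-facing clinician who stays blind is a plausible reviewer. What stands is that nothing requires a blinded one.
- **The data start from subjects.** Rehabilitation and corrective procedures begin with yes/no questions, the second about what the surgeon told the subject. A reader might conclude that the appendix's rationale is simply false for three endpoints. That goes too far: it speaks of major endpoints, an undefined term, and analgesic classification needs little judgement. But all nine endpoints are co-equal and a review decides which entries count, so the rationale does not clearly cover these three.
- **Earlier release of A4091056 and A4091057.** Because these studies are shorter, a reader might infer a long period of unblinded review. Unblinding is by parent study and both are placebo-controlled, so their release does not reveal A4091058 arms.
- **Safeguards exist.** Sites stay blind, the non-drug review is logged, and many decisions may be made before A4091058 release. This protects data collection and part of the classification, but not what is reviewed later.
- **Descriptive analysis only.** The absence of testing removes error-rate concerns, but not bias in the described difference between arms. The appendix's statement that design, conduct and analysis will not change because of parent results does not govern classification of individual entries.
- **The SAP discloses the unblinding.** It links the plan to Protocol 5, and Protocol 9 lets the SAP modify planned analyses. The sponsor may also read direct involvement as site-facing work. Neither text clearly says so, and Protocol 9 does not clearly extend to the blind.

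**Conclusion.** The point holds in two parts. First, Protocol 5 and SAP Appendix 2 section 4.1 are inconsistent as written; confidence in this is high. Second, SAP 6.1 leaves reviews affecting 3 of 9 co-equal endpoints open after A4091058 may have been unblinded, with no blinded-reviewer requirement, although the first-symptom review has an earlier closing point. Confidence that this leaves avoidable room for classification bias is moderate, and it is strongest for rehabilitation and corrective procedures.

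The size cannot be estimated. It depends on who reviews, how many entries are decided after A4091058 release, and how much judgement they need, none of which is given. The 1.7 to 3.3 points per subject rest on an assumed 30 to 60 subjects per arm and show only how much one decision weighs; they are not evidence that decisions would differ by arm. The change should be made because it is cheap and protects the one comparison among the objectives.

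**What to change.** 1. **SAP 6.1.** Require the rehabilitation, corrective-procedure and analgesic-use reviews to be done by qualified existing staff blinded to individual parent treatment, whether or not they hold a section 4.2 role, on listings without treatment codes. Log decisions and finalise them before the data enter any by-arm output available to the study team. Except the DMC outputs, which a separate unblinded group produces under SAP 3. Flag any decision made or changed by an unblinded person.
2. **SAP Appendix 2, section 2.** Limit the first rationale to endpoints that are not determined by review.
3. **SAP Appendix 2, section 4.2, and Protocol 5.** State that the section 4.2 blind runs to A4091064 database release. Reconcile Protocol 5 with section 4.1 by naming the roles that may be unblinded, and when.

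The cost is wording in the SAP and protocol, with no new data. The downside is that it limits which existing staff can do the reviews. Closing all the reviews before parent unblinding is not a workable alternative, because some subjects may still be in follow-up then.

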4.2 Blinded until Database Release of final phase 3 study

At the time of database release/unblinding for reporting of each parent study, Pfizer/Syneos/EPS roles of A4091064 study in below lists are to remain blinded of individual subject level in order to maintain the integrity of the blinding to subjects and investigators;

- Pfizer: Clinician interacting with site directly for TJR evaluation, and regional clinical site lead (RCSL);
- Syneos/EPS(Japan Local CRO): Clinical research associate, monitoring lead, CTA, and CMPL.

An investigator site (investigators, and all other site staff) participating in A4091064 is to remain blinded to individual subject treatment assignment until all subjects in the site will be finished A4091064 and until all data for these subjects will be cleaned.

Pfizer SOPs CT20 (Public Disclosure of Pfizer Clinical Study Data and Authorship) and DMB10 (Clinical Study Report) require unblinded results to be provided to study sites after the trial has completed. Some amendment/deviation may be applied to delay sending results from the parent studies or sub-studies until a site has completed participation of all subjects in the site of A4091064.

Selected investigators may be required to review an interim CSR for A4091064 in order to sign the Investigator's Declaration. In order to minimize any potential bias after unblinding of any parent study, an investigator will be selected who would not have any on-going A4091064 subjects at the time of the investigator's review of an interim A4091064 CSR.

It is also recognized that unblinded summary results may become publicly known through press release, presentations at scientific conference, publication and so on.
